### **Research Aims:**

The aim of this randomized pilot trial is to evaluate the acceptability, feasibility, and efficacy of CPS delivered by phone calls or text messages to AYAs with several distinct chronic illnesses, in preparation for a fully-powered multisite, effectiveness-implementation hybrid trial. We propose 1) assessing the feasibility, acceptability, and efficacy of CPS for improving

medication adherence, 2) investigating the impact of delivering CPS through live text messages versus phone calls using quantitative and qualitative methods, and 3) evaluating patient and provider views of CPS to guide future implementation work. The proposed research follows the conceptual model (Figure 1), positing that CPS will promote adherence through engaging AYAs in calls or texts with a human coach providing social support. We predict that delivering CPS by text message will increase feasibility and acceptability, perceived social support, and medication compared to voice delivery. This study extends the literature on mHealth to promote AYA adherence in several ways. First, although increasingly interactive and personalized *automated* text message interventions are proliferating in the adherence literature, there have been no randomized trials published evaluating the impact of *live* text message conversations on medication adherence among AYA. Second, rather than focusing on a single focal diagnoses, this study will enroll AYA with *diverse* chronic illnesses. This approach could greatly increase the number of patients having access to self-management support, therefore leading to a greater reduction in negative healthcare outcomes, costs, and burden. Third, despite comprising over 20% of the US AYA population, Latinx patients make up only 5% of mHealth study samples (e.g., DeKoekkoek et al., 2015). The proposed study will enroll >50% Latinx participants, based on pilot data, increasing national representativeness of the mHealth iteration [4].

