### ***Primary Outcomes: Adherence Dependent Variables***

**Self-Reported Adherence.** In this study, medication adherence over the past 3 months was measured by a 3-item visual analogue scale (VAS) developed by Walsh, Dalton, and Gazzard (1998). The VAS uses percentage scales that contains the percent (%) value from 0 to 100 in which each point on the scale suggests the percent of time of medication adherence within a specified duration of time: 0% would mean “none of the time” or “never”; 50% would mean half of the time; 100% would mean “all of the time” or “always”, and numbers in between would mean amounts between “never” and “always” (Walsh, Dalton, & Gazzard, 1998). For each time frame, three visual analogue scales are provided, assessing 1) the percentage of the time patients took their medicine, 2) the percentage of the time patients took all the doses for the day, and 3) the percentage of the time patients took their medicine according to the directions (Walsh, Dalton, & Gazzard, 1998). Administering self-report adherence surveys by computer may decrease social desirability bias (Stirratt et al., 2015).

**MEMS Caps Adherence.** Participants (and caregivers, in the case of minor participants) will be oriented to using MEMS caps for one of the medications they take daily of their focal diagnosis (i.e., immunosuppressant for transplant, antiepileptic drug for epilepsy, hydroxyurea for sickle cell disease, metformin for type 2 diabetes). Microelectronic circuitry records the dates and times the caps are opened. We will calculate the percentage of prescribed doses that appear to have been taken through week 6, 12 and 18. MEMS caps are considered the “gold standard” in

adherence research and show moderate validity with both patient populations (Gerson et al., 2004; Cramer et al., 1995).

**Electronic Health Record Adherence Indicators.** Many of the focal diagnoses have regular labs collected as part of usual clinical care. For example, medication trough levels are usually collected periodically for the purpose of therapeutic drug monitoring for AYA living with solid organ transplants (i.e., immunosuppressant medications) and epilepsy (i.e., anti-epileptic drugs.). For other diagnoses, regularly collected labs are considered partially indicative of adherence, such as the hemoglobin A1C test for type 2 diabetes and mean corpuscular volume/fetal hemoglobin for sickle cell disease.

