## **Analytic Plan**

We will begin by examining the distribution and missingness of our outcome of interest, VAS. To take advantage of every available data point and account for repeated measures clustered within individual participants, we will run mixed-effect models in {STATA/SAS/R}, using a nested model-building process. If VAS is normally-distributed, we will specify linear mixed-effects models; otherwise, we may need to transform or dichotomize the outcome to ensure model assumptions are met. We will first run a simple model with only time (0, 6, 12, 18 weeks) as a Level I fixed effect predictor and VAS as a dependent variable, with the participant identification number included as a Level II random effect due to intra-individual correlation of VAS over time. Then, we will run increasingly complex models with intervention assignment (Cell Phone Support calls or texts n = 40 versus automated text reminders n = 20) included as a Level II fixed effect predictor, and then sex assigned at birth, focal medical diagnosis, medication complexity, age, and racial/ethnic identity as Level II fixed effect predictors, as well, to adjust for known or theoretical covariates. I will examine the impact of including increasing number of hypothesized predictors on model fit by examining AIC and  $R^2$ , and pare down the model if the model fit does not improve with all the hypothesized predictors included. This will lead to presenting parsimonious models that estimate the independent effect of the intervention on outcomes of interest, adjusted for all other predictors in the models. Finally, I will also assess whether model assumptions were met by plotting residuals versus fitted values. When I am

confident I have developed the most parsimonious, best-fitting model, I will calculate effect size estimates for the average difference in mean VAS between the Cell Phone Support call and text groups ( $n = 40$ ) and the automated text reminder group ( $n = 20$ ).

Then, we will follow the sample approach to predicting MEMS Caps adherence outcomes, and depression, social support, and self-efficacy. We will also run exploratory analyses using electronic-health record abstracted values (e.g., immunosuppressant levels, anti-epileptic drug levels, hemoglobin A1C, mean corpuscular volume/fetal hemoglobin) within focal diagnosis groups.

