### **Power Analysis**

Using STATA SE Version 15 software, we estimated the statistical power achieved with our proposed sample, assuming the Cohen's  $d$  effect size of 0.85 between groups seen in our preliminary data, within-subject intra-class correlation of 0.5 for repeated measures. We used the

design effect for clustered data (3 post-baseline measures, intraclass correlation=0.5) to compute the effective sample size for each group. The table below shows estimated power to detect differences in CPS (combined) versus automated reminders, and for the comparison of CPS strategies (original vs live text) in the total sample and by medical condition. To be more conservative, we also provide the statistical power for the CPS comparisons with a smaller effect size of 0.75 and 0.50. We also computed power to detect simple pre/post (e.g., baseline-12 week) changes between groups. There is approximately 87% statistical power for group comparisons using the combined sample with the effect size of 0.85; power is reduced for subgroup comparisons and the smaller effect size. However, as this study is a pilot randomized trial, the sample is more than sufficient to estimate effect sizes and assess feasibility for use in future proposals. See Table 1 for details.

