Cell Phone Support to Promote Medication Adherence Among Adolescents and Young Adults With Chronic Illness

NCT04241627

8/8/2022

This randomized pilot trial tested three different digital health interventions against one another (CPS-C, n = 11, CPS-T, n = 12, and ATR, n = 11). We are interested in the impact on self-reported medication adherence. We have 6 different measures of dependent variables (VAS1w, VAS2w, VAS3w, VAS1m, VAS2m, VAS3m). We assessed our dependent variables 4 occasions, at 0 weeks (pre-tx), 6 weeks (mid-tx), 12 weeks (post-tx), and 18 weeks (follow-up). We would like to run mixed-effect models to test for intervention effects of 1) both CPS conditions (CPS-C and CPS-T, n = 23) versus ATR (n = 11); and 2) the CPS conditions against each other, ignoring ATR (CPS-C, n = 11 versus CPS-T, n = 12). I also have covariates (sex assigned at birth, diagnosis, age) that we can include during nested model building procedures, and include in final reported models if they lead to best fit.

Can we begin by examining the distributions of our dependent variables, and discuss whether we should use linear mixed-effects models; otherwise, we may need to transform or dichotomize the outcome or use a different type of model (poisson? Negative binomial?) to ensure model assumptions are met?

Then, can we evaluate the impact of missing data on my results by re-running these analyses using inverse probably weighting. It is possible that missing data will not be completely at random (i.e., participants with lower medication adherence may also be less likely to adhere to the online survey schedule).

Finally, I would like to calculate effect sizes for subgroups (see the final table). See tables on the next pages.

Blank Tables

Table 5

Best-Fitting Models Predicting Self-Reported Adherence for Both CPS Conditions (C and T) versus ATR (N = 34)

Dependent Variables	VAS1w			VAS2w			VAS3w			VAS1m			VAS2m			VAS3m		
	Estimates	CI	p															
Fixed Effects																		
Intercept																		
Time																		
Intervention Group (both CPS versus ATR)																		
Random Effects																		
σ^2																		
τ_{00}																		
τ_{11}																		
ρ_{01}																		
ICC																		
N																		
Observations																		
Marginal R ² / Conditional R ²																		
AIC																		

Note—Make ATR the reference group so the estimate tells us how the combined CPS groups compare

Table 6

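### The protocol names one past-3-month VAS outcome, but the SAP tests six past-week and past-month scores with no lead score, so the efficacy result is open to selection

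*SAP*

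**What the plan says.** **Protocol.** The Self-Reported Adherence paragraph under Primary Outcomes states: "In this study, medication adherence over the past 3 months was measured by a 3-item visual analogue scale (VAS". The same paragraph adds "For each time frame, three visual analogue scales are provided", but it does not list the time frames or say how the three items are combined. The Analytic Plan starts by "examining the distribution and missingness of our outcome of interest, VAS" and treats VAS as one variable throughout. Its group contrast is "Cell Phone Support calls or texts n = 40 versus automated text reminders n = 20". The comparison of the two CPS modes is a separate aim in Research Aims: "investigating the impact of delivering CPS through live text messages versus phone calls using quantitative and qualitative methods".

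**SAP.** The analysis request states: "We have 6 different measures of dependent variables (VAS1w, VAS2w, VAS3w, VAS1m, VAS2m, VAS3m". The titles of Tables 7 and 8 show that the suffixes w and m mean past week and past month. No past-3-month score appears. Table 5 is titled "Best-Fitting Models Predicting Self-Reported Adherence for Both CPS Conditions (C and T) versus ATR (N = 34", and Table 6 repeats the layout for CPS-T versus CPS-C. Both provide an estimate, CI and p for each of the six scores. Their fixed-effect rows are an intercept, Time and Intervention Group, with no interaction. Tables 7 and 8 are labelled exploratory; Tables 5 and 6 are not.

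Neither document names a lead score, a composite, a significance level or a multiplicity rule.

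**The concern.** The one recall window that the protocol names is absent from the SAP, and the two windows that the SAP analyses are not named in the protocol. A reader cannot tell which window, or which of the three items, answers the efficacy question.

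Six parallel p-values for the same contrast raise the chance that at least one crosses 0.05 when nothing is going on. Picking the largest of six estimates also biases the effect size upward. That matters here because the Power Analysis section justifies the sample by saying that "the sample is more than sufficient to estimate effect sizes and assess feasibility for use in future proposals". The effect size is a main product of this pilot, and a proposal that quotes one figure would not reveal that there were six to choose from.

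**Working it through.** **Inputs from the documents.** Six scores; CPS n = 23 versus ATR n = 11 (SAP); within-subject ICC 0.5 (Power Analysis); assessments at weeks 0, 6, 12 and 18.

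**Assumed.** Two-sided 0.05 per test; equal correlation r between scores at one occasion, from 0.7 to 0.9; normal scores; complete data; no covariate or model-form selection.

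**The plan's own figure.** The documents give no error rate for the six scores. The stated power of about 87% is the only check on the significance level. At 40 versus 20 and d = 0.85, 0.85/√(1/40 + 1/20) = 3.10, and Φ(3.10 − 1.96) = 0.87. That fits two-sided 0.05. It is indirect support only, because the design-effect method which that section describes would give about 97%.

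**Step 1: single occasion.** The chance of at least one |Z| > 1.96 among six equally correlated scores is

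1 − ∫ φ(u) [Φ((1.96 − √ρ·u)/√(1−ρ)) − Φ((−1.96 − √ρ·u)/√(1−ρ))]⁶ du.

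With ρ = r this gives 16.4%, 13.9% and 10.8% for r = 0.7, 0.8 and 0.9. Simulated pooled t-tests at 23 versus 11 give the values in the table below. Outside the assumed range, the formula gives 20.7% at r = 0.5 and 8.9% at r = 0.95.

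**Step 2: four occasions.** Take a random-intercept model with a Group main effect. With complete data, the Group coefficient is the difference between arms in person means over the four occasions. Set the variance of a score at one occasion to 1. The ICC of 0.5 splits it into 0.5 between persons and 0.5 within. A person mean then has variance 0.5 + 0.5/4 = 0.625. The correlation ρ between two scores' person means depends on where the item-specific part, 1 − r, sits:

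- occasion noise: ρ = [0.5 + (r − 0.5)/4]/0.625
- stable within a person: ρ = [(r − 0.5) + 0.125]/0.625

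These ρ go into the Step 1 formula.

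| r | t-tests, any p<0.05 | of which favouring CPS | ρ, noise | four occasions, noise | ρ, stable | four occasions, stable |
|---|---|---|---|---|---|---|
| 0.7 | 16.7% | 8.4% | 0.88 | 11.5% | 0.52 | 20.3% |
| 0.8 | 14.2% | 7.1% | 0.92 | 10.1% | 0.68 | 16.9% |
| 0.9 | 11.0% | 5.5% | 0.96 | 8.4% | 0.84 | 12.7% |

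One fixed score has a nominal 5%, or 2.5% in favour of CPS.

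**Step 3: largest of six estimates.** In the single-occasion simulation with true d = 0.50, the largest of six averages 0.79, 0.74 and 0.67 (r = 0.7, 0.8, 0.9), against 0.51 for one score.

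Tables 5 and 6 work differently, because their Group coefficient includes week 0. An effect of 0.50 at weeks 6, 12 and 18 and none at week 0 has expectation (0 + 0.50 + 0.50 + 0.50)/4 = 0.375. The largest of six is then about 0.375 + 1.267 × √(0.625(1 − ρ)) × √(1/23 + 1/11), where 1.267 is the expected maximum of six independent standard normals and the last root is 0.367. For ρ = 0.96 this is 0.375 + 0.073 = 0.45. For ρ = 0.52 it is 0.375 + 0.254 = 0.63.

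**The case against.** - **This is a pilot with no decision rule based on significance, and all six columns are to be shown.** This stands. A careful reader of the completed tables would see the pattern across scores. The harm needs someone to quote one score, and nothing in either document says that the largest or most significant will be chosen.
- **Three scales per time frame were foreseen, and the items are facets of one instrument.** This stands in part. It explains three items per window and suggests that more than one window was administered. It does not explain why the only named window drops out, and it does not say which score leads.
- **The numbers rest on assumptions.** This stands. Neither the significance level nor r is in the documents, so no single percentage can be treated as the trial's error rate. A reader might also add the CPS-T versus CPS-C tests and quote 21% to 31% for all twelve, but the protocol treats that comparison as a separate aim.
- **The effect-size inflation is overstated.** A reader might infer that a true 0.50 would appear in Table 5 as 0.67 to 0.79. The documents do not support that. Those are single-occasion illustrations, and the tabulated main effect is diluted by week 0. Within the SAP, d appears only in the exploratory Tables 7 and 8, although the Analytic Plan does promise an effect size from the final VAS model.
- **The 5% benchmark is optimistic.** This also stands. Covariates and model form are to be chosen by fit, so even one lead score has 5% only before that selection.

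A reader might also infer that scores were switched or picked after results were seen. The documents do not show this: the SAP lists all six and asks to start from their distributions.

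**Conclusion.** The concern holds. The mismatch in recall window, the six separately modelled scores and the absence of a lead score are plain in the text. Their size is less certain. At an assumed two-sided 0.05 and r of 0.7 to 0.9, the chance of at least one p<0.05 for CPS versus ATR under no effect is about 11% to 17% for single-occasion t-tests. It is about 8% to 20% for the four-occasion main-effect model. About half of these results favour CPS.

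The four-occasion range rests on ICC 0.5, complete data and a random intercept only, as in the Analytic Plan. Tables 5 and 6 also have rows for a random slope, which would alter it.

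Taking the largest of six estimates biases the effect upward, while including week 0 pulls it down. The two do not reliably cancel: 0.45 to 0.63 lies on both sides of a true 0.50. The sponsor should correct this, but it does not invalidate the pilot.

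**What to change.** 1. Reconcile the recall window in both documents with the survey actually administered.
2. Name one lead score, for example the mean of the three items for one window, for CPS combined versus ATR. Use the same score for CPS-T versus CPS-C as a separate secondary question.
3. Define the lead contrast as post-baseline, at a stated time point or as a stated average. Obtain it with a group-by-time term or baseline adjustment. This is needed whichever summary is chosen, not only for a single week, because the Group row in Tables 5 and 6 includes week 0.
4. Report the other scores as supportive estimates with CIs, with no claims from their p-values.
5. Label the choice post hoc if group comparisons have already been seen.

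**Cost.** No new data. Tables 5 and 6 gain a lead-score column and an interaction or baseline row. The p-values for single items and for the other window no longer support claims. A three-item mean can hide differences between taking the medicine at all, taking every dose and following the directions.

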## **Design**

After passing eligibility screening and completing pre-treatment questionnaires, participants will be randomly assigned (1:1:1) to one of three 12-week groups: CPS delivered through voice-based phone calls (CPS-C), CPS delivered through text messaging (CPS-T), or automated text message reminders (Automated Reminders). A research colleague outside of the team used rand( ) function in Excel to create randomization blocks of 6 by sex assigned at birth and focal diagnosis. I hope to prevent substantial confounding by using stratified block randomization. For example, among the first 6 female participants with organ transplants, 2 would be assigned to CPS-C, 2 would be assigned to CPS-T, and 2 would be assigned to ATR.

The research colleague placed cards in sealed envelopes indicating the group assignment, and after the participant signed the consent form, the PI opened the envelope and informed the participant of the group they had been assigned to.

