Best-Fitting Models Predicting Self-Reported Adherence for CPS-T versus CPS-C (N = 23)

Dependent Variables	VAS1w			VAS2w			VAS3w			VAS1m			VAS2m			VAS3m		
	Estimates	CI	p															
Fixed Effects																		
Intercept																		
Time																		
Intervention Group (CPS-T versus CPS-C)																		
Random Effects																		
σ^2																		
τ_{00}																		
τ_{11}																		
ρ_{01}																		
ICC																		
N																		
Observations																		
Marginal R ² / Conditional R ²																		
AIC																		

Note—Make CPS-C the reference group so the estimate tells us how CPS-T compares

Table 7

Exploratory Analyses Estimating Effect Sizes Using Self-Reported Outcomes Past Week (Pre-Post... Baseline to 12 weeks)

Subgroup	n	d	CI	p	Subgroup	n	d	CI	p
VAS1w									
Total Sample	--	--	--	--	Young Men	--	--	--	--
CPS Combined vs. ATR	34				CPS Combined vs. ATR				
CPS-T vs. CPS-C					CPS-T vs. CPS-C				
Sickle Cell Disease	--	--	--	--	Young Women	--	--	--	--
CPS Combined vs. ATR	14				CPS Combined vs. ATR				
CPS-T vs. CPS-C					CPS-T vs. CPS-C				
Solid Organ Transplant	--	--	--	--	Latinx	--	--	--	--
CPS Combined vs. ATR	10				CPS Combined vs. ATR				
CPS-T vs. CPS-C					CPS-T vs. CPS-C				
Type 2 Diabetes	--	--	--	--	Black	--	--	--	--
CPS Combined vs. ATR	10				CPS Combined vs. ATR				
CPS-T vs. CPS-C					CPS-T vs. CPS-C				
VAS2w									
Total Sample (N = 34)	--	--	--	--	Young Men	--	--	--	--
CPS Combined vs. ATR					CPS Combined vs. ATR				
CPS-T vs. CPS-C					CPS-T vs. CPS-C				
Sickle Cell Disease (n = 14)	--	--	--	--	Young Women	--	--	--	--
CPS Combined vs. ATR					CPS Combined vs. ATR				
CPS-T vs. CPS-C					CPS-T vs. CPS-C				
Solid Organ Transplant (n = 10)	--	--	--	--	Latinx	--	--	--	--
CPS Combined vs. ATR					CPS Combined vs. ATR				
CPS-T vs. CPS-C					CPS-T vs. CPS-C				
Type 2 Diabetes (n = 10)	--	--	--	--	Black	--	--	--	--
CPS Combined vs. ATR					CPS Combined vs. ATR				
CPS-T vs. CPS-C					CPS-T vs. CPS-C				
VAS3w									
Total Sample (N = 34)	--	--	--	--	Young Men	--	--	--	--
CPS Combined vs. ATR					CPS Combined vs. ATR				
CPS-T vs. CPS-C					CPS-T vs. CPS-C				
Sickle Cell Disease (n = 14)	--	--	--	--	Young Women	--	--	--	--
CPS Combined vs. ATR					CPS Combined vs. ATR				
CPS-T vs. CPS-C					CPS-T vs. CPS-C				

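### Tables 5 and 6 fit one constant group effect over weeks 0, 6, 12 and 18, so off-treatment week 18 is mixed with on-treatment visits and the week-18 difference is never estimated

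*SAP*

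**What the plan says.** The protocol's Design section fixes the length of treatment: "participants will be randomly assigned (1:1:1) to one of three 12-week groups". Its Procedures section and the SAP's opening text both label week 12 as post-treatment and week 18 as follow-up. The SAP lists all four visits as outcome occasions: "We assessed our dependent variables 4 occasions, at 0 weeks (pre-tx), 6 weeks (mid-tx), 12 weeks (post-tx), and 18 weeks (follow-up").

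The protocol's Analytic Plan starts from time alone: "We will first run a simple model with only time (0, 6, 12, 18 weeks) as a Level I fixed effect predictor". Intervention assignment is then added as a participant-level predictor, followed by covariates. The target is a mean difference in VAS between the groups, with no visit named.

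The SAP's Table 5 and Table 6 shells have three fixed-effect rows: the intercept, Time, and one group row. The group row is "Intervention Group (both CPS versus ATR") in Table 5 and "Intervention Group (CPS-T versus CPS-C") in Table 6. Both shells also have random-effect rows for a slope variance and an intercept-slope correlation.

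Table 7 uses a different window: "Exploratory Analyses Estimating Effect Sizes Using Self-Reported Outcomes Past Week (Pre-Post... Baseline to 12 weeks"). Table 8, for the past-month items, states no interval.

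**The concern.** With one group row and no group-by-time term, the model assumes the same group difference at every visit. That cannot hold at week 0, where randomised groups differ only by chance. At week 18 it holds only if the effect fully outlasts the coaching, the reminders and the monthly incentive. The VAS items in Tables 7 and 8 look back a week or a month, so at week 18 their recall periods lie wholly after treatment.

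The protocol says the pilot prepares for a fully powered trial and that its sample will supply effect sizes. A pooled coefficient serves that purpose badly. Averaged over weeks 6, 12 and 18 with equal weights, an effect of 1, 1, 0 and a constant effect of 0.67 give the same number, although they would lead to different designs for the next trial. A single straight Time term also cannot show a rise on treatment followed by a fall.

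**Working it through.** **The plan's own figure.** The documents give no figure for dilution. The nearest one is the power of about 87% in the Power Analysis section, at d = 0.85. With 40 v 20, one measurement per person and two-sided alpha 0.05 (assumed), SE = √(1/40 + 1/20) = 0.274 and power = Φ(0.85/0.274 − 1.96) = 0.874, which matches. The design-effect route described in the text, with three post-baseline measures and ICC 0.5, gives 1 + 2 × 0.5 = 2, effective sizes of 60 v 30, and power 0.967. Both routes use one effect size, with no allowance for fading.

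**Inputs.** Visits at weeks 0, 6, 12 and 18 (SAP); ICC 0.5 (protocol, Power Analysis); 23 v 11 and 12 v 11 (SAP). Assumed: complete data, outcome SD 1, true effect 0 at week 0, 1 at weeks 6 and 12, and k at week 18. The documents do not give k, so a range is shown.

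**Formula.** With complete data, the group coefficient in a Time + Group mixed model is a weighted sum of the visit-specific differences. The weights are w = V⁻¹1 / (1′V⁻¹1), where V is the within-person covariance matrix.

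**Random intercept.** Each of the four visits has weight 0.25, so the coefficient is 0.25 × (0 + 1 + 1 + k).

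| Effect left at week 18 | Four visits, as planned | Weeks 6, 12, 18 only |
|---|---|---|
| k = 1 (persists) | 0.75 | 1.00 |
| k = 0.5 (halves) | 0.63 | 0.83 |
| k = 0 (gone) | 0.50 | 0.67 |

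Week 0 alone costs a quarter. Full fade at week 18 takes the coefficient from 0.75 to 0.50, a relative loss of 0.25/0.75 = one third. Removing week 0 leaves the same one-third loss.

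**Random slope, as in the shells.** The weights then lie on a straight line in time. Weeks 6 and 12 together always hold 0.50, so full fade always gives 0.50. The value under persistence is 1 − w₀, which depends on the slope variance and correlation. With intercept and residual variances of 0.5 each and assumed slope SDs per week:

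| Slope SD, correlation | Weight, week 0 | Weight, week 18 | Persists | Gone | Relative loss from week 18 |
|---|---|---|---|---|---|
| 0.02, −0.5 | 0.195 | 0.305 | 0.81 | 0.50 | 38% |
| 0.02, 0 | 0.307 | 0.193 | 0.69 | 0.50 | 28% |
| 0.04, 0 | 0.414 | 0.086 | 0.59 | 0.50 | 15% |
| 0.06, 0 | 0.504 | −0.004 | 0.50 | 0.50 | about none |

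At an extreme setting (0.06, correlation 0.5) the week-18 weight is −0.17. Week 18's share therefore cannot be fixed from the documents. As its weight falls, the weight on week 0 rises.

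**Precision of single-visit contrasts.** For 23 v 11, SE = √(1/23 + 1/11) = 0.37, a 95% half-width of 1.96 × 0.367 = 0.72 SD. For 12 v 11, SE = 0.42 and the half-width is 0.82. Using baseline with correlation 0.5 multiplies these SEs by √(1 − 0.25) = 0.87, giving 0.32 and 0.36. The planned four-visit coefficient has SE 0.367 × √((1 + 3 × 0.5)/4) = 0.29 for 23 v 11.

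That smaller SE belongs to a smaller quantity. With an on-treatment effect of 1 SD, effect over SE is 0.75/0.290 = 2.6 for the planned coefficient if the effect persists, and 0.50/0.290 = 1.7 if it is gone. It is 1/0.367 = 2.7 for week 12 alone and 1/0.317 = 3.1 for week 12 with baseline used.

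**The case against.** The best defence is that an average over follow-up was intended. The protocol targets a mean difference without naming a visit, its power calculation counts three post-baseline measurements (which include week 18), and durability is not among the stated aims. This stands in part: averaging over follow-up is a legitimate choice. It does not explain why week 0 is in the average, and it leaves the week-18 difference unreported although the data are collected.

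A second defence is that Table 7 already plans a baseline-to-12-week effect size, with confidence interval and p-value, for the total sample, both contrasts and all three past-week items. This also stands. A reader might infer that the SAP never estimates the effect of 12 weeks of treatment, or that it contradicts itself by using two windows. Neither follows, since two labelled analyses may use different windows. But Table 7 is exploratory and covers the past-week items only, and Table 8 gives no interval.

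A third is that no document says how much of the effect fades, so the size is hypothetical. That is correct, and it is why a range is given. It is also a reason to estimate the week-18 difference.

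Finally, the model building might be thought to leave room for a group-by-time term. The candidate predictors listed in both documents are participant characteristics, and the effect modifiers mentioned in the Analytic Plan are measured covariates. Visit is not among them.

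**Conclusion.** The structural point holds. Tables 5 and 6 estimate one time-constant difference that mixes weeks 6 and 12 with off-treatment week 18 and pre-treatment week 0, and no planned self-report analysis isolates week 18.

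Under a random intercept, ICC 0.5, complete data and an equal effect at weeks 6 and 12, the coefficient is 0.75, 0.63 or 0.50 of the on-treatment effect as the week-18 effect persists, halves or vanishes. Week 18's own part is a one-third relative loss at full fade. Under the random slopes in the shells it runs from about none to slightly over a third, depending on variances the documents do not give.

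A reader might infer that dilution is capped at a third. The documents do not support that. A third is the equal-weight value, it can be exceeded slightly, and the total shortfall from the on-treatment effect reaches one half because week 0 is pooled as well. Nor do the documents show that the effect does fade. The fault lies in what the models can report, whatever the result.

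**What to change.** In Tables 5 and 6, replace the single Time and Intervention Group rows with visit as a categorical factor and group-by-visit terms. Constrain baseline to be equal across arms, or use it as a covariate, so that week 0 is handled in the same model. Then:

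- name the week-12 group difference as the single main effect, matching Table 7;
- report the week-18 difference in a separate row, labelled as descriptive evidence on persistence, with its confidence interval;
- state the same baseline-to-12-week interval for Table 8.

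The cost is SAP wording and longer tables, because several visit terms replace one Time row. The main confidence interval will be wider than for an average over visits: without using baseline, SE 0.37 for week 12 against 0.30 for the mean of the three post-baseline visits (0.367 × √(2/3)). At N = 34 the week-18 estimate will be imprecise (SE about 0.37 SD for 23 v 11, or about 0.32 if baseline correlates 0.5) and should be read as an interval rather than a test. No new data are needed.
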